11. ADMINISTRATIVE AND LEGAL CONSIDERATIONS

11.1 General Legal Requirements

11.2 Ethical approvals

The ICL RGIT CTIMP Committee have confirmed that this study does not require MHRA authorisation.

The Study Coordination Centre has obtained approval from the London - West London & GTAC Research Ethics Committee Research Ethics Committee (REC) and Health Research Authority (HRA). The study must also

receive confirmation of capacity and capability from each participating NHS Trust before accepting participants into the study or any research activity is carried out. The study will be conducted in accordance with the recommendations for physicians involved in research on human subjects adopted by the 18th World Medical Assembly, Helsinki 1964 and later revisions.

11.3 Informed consent

Consent to enter the study must be sought from each participant only after a full explanation has been given, an information leaflet offered and time allowed for consideration. Signed participant consent should be obtained. The right of the participant to refuse to participate without giving reasons must be respected. After the participant has entered the study the clinician remains free to give alternative treatment to that specified in the protocol at any stage if he/she feels it is in the participant's best interest, but the reasons for doing so should be recorded. In these cases the participants remain within the study for the purposes of follow-up and data analysis. All participants are free to withdraw at any time from the protocol treatment without giving reasons and without prejudicing further treatment.

11.4 Patient confidentiality

Participants' identification data will be required for the registration process. The Study Coordination Centre will preserve the confidentiality of participants taking part in the study and is registered under the Data Protection Act.

The site Investigators affirm and uphold the principle of the subject's right to protection against invasion of privacy. Personal health data will be kept confidential.

On paper CRFs or other documents, subjects will be identified by their subject ID only. However, each site Investigator will keep in his/her file a Subject Identification List. With respect to the processing of data, every subject has to agree with this in writing. This agreement should be documented together with the written informed consent for trial participation.

The Chief Investigator will preserve the confidentiality of participants taking part in the study and is registered under the Data Protection Act.

Data will be pseudonymised

11.5 Protocol Amendments

Any changes in the protocol will require a formal approval.

11.6 Premature Termination of the Study

The Chief Investigator reserves the right to terminate the trial for well-documented reasons.

Further recruitment of subjects will not take place under the following conditions:

- Premature termination of the trial.
- Drug-related events, i.e. SUSARs, emerging AEs that are serious and the risk/benefit ratio is unacceptable.
- Procedure-related events, i.e., the recruitment rate is too low or the number of dropouts for administrative reasons is too high.
- The model predicts that the lowest dose has a toxicity above the TTL with 90% certainty.

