4.1 Overall study design and plan

Patients will be invited to participate by their local pulmonary hypertension hospital. The first 2 participants will be treated with XBD173 90mg once daily for 8 weeks. The first patient will be followed for at least 2 weeks before the second patient starts the XBD173. Subsequent participants will be treated with XBD173 90mg once daily for 2 weeks at intervals of at least 2 week and if the drug is tolerated (defined as an absence of grade 2 adverse events) the dose will be increased to 90mg twice daily for a further 6 weeks. The total period of treatment for each patient is 8 weeks, followed by 4 weeks follow up off XBD173. If a grade 2 AE occurs during 90mg once daily dosing, the participant will be withdrawn. If a patient does not tolerate 90mg twice daily, the local PI will determine whether to stop XBD173, reduce the dose to 90mg once daily or pause dosing and restart at 90mg once daily.

The starting dose of 90mg OD is based on experience from studies of XBD173 in healthy volunteers and in patients with multiple sclerosis.

Rupprecht et al randomised 71 healthy volunteers to 7 days treatment with placebo, 10, 30, or 90 mg/day XBD173 or 2 mg/day alprazolam (PMID: 19541954). The number of side effects reported with XBD173 was comparable to the incidence in the placebo group. In contrast, a much higher incidence was reported by the alprazolam-treated group.

In addition, 4 studies have been sponsored by Imperial College London using XBD173. In all studies XBD173 was well tolerated with no SAEs:

17/LO/0566. This study recruited healthy volunteers (n=31) and people with MS (n=12) and administered XBD173 90mg for 7 days. (To be submitted for publication September 2022).

14/LO/0343. This study recruited people with MS (n=6) and administered a single dose of XBD173 (90mg) prior to PET scanning with 11C-GE180. (PMID: 30796709).

12/LO/0735. This study recruited healthy volunteers (n=6) and administered a single dose of XBD173 ranging from 10mg-90mg prior to PET scanning with 11C-PBR28. (PMID: 24623083).

13/LO/1916. This study recruited healthy volunteers (n=6) and people with MS (n=6) and administered a single doses of XBD173 (90mg) prior to PET scanning with 11C-PBR28. (PMID: 30796709)

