4.3.4 Discontinuation criteria

It is possible that the Sponsor, REC or HRA request termination of the study if there are concerns about conduct or safety, or due to a change in the opinion of the Ethics Committee.

When the Sponsor is aware of information on matters concerning the quality, efficacy, and safety of the study drug, as well as other important information that may affect proper conduct of the clinical study, the Sponsor may discontinue the clinical study and send a written notice of the discontinuation along with the reasons to the Investigators. Patients will be informed that they have the right to withdraw from the study at any time for any reason, without prejudice to their medical care. The site Investigator/Chief Investigator can discontinue subjects from the study for any of the following reasons:

1. Occurrence of an unacceptable Adverse Event due to Grade 2 or above defined by the NCI Common Terminology Criteria for Adverse Events (version 5.0, 2017), adapted for this study -see [Appendix 2](#).
2. Subject request
3. Subject is lost to follow-up
4. Administrative reasons
5. Development of an intercurrent illness, condition, or procedural complication, which would interfere with the subject's continued participation
6. Patient becomes pregnant

The site Investigator/Chief Investigator also reserves the right to discontinue subjects in the interest of subject safety and welfare. Investigators must contact all participants and the hospital pharmacy (where applicable) to notify them of the termination of the study. In cases of an early termination (discontinuation), a follow-up telephone assessment will be performed 4 weeks \pm 3 days -see [Appendix 1](#).

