4.3.5 Subject identification and replacement policy

After informed consent is obtained, patients who are screened will be assigned a 7-digit permanent identification number (subject ID) such that all patients given consecutive identification numbers in successive order of inclusion. The first 4 digits of the will be the designated research site ID, and the last 3 digits will be assigned at the research study centre (e.g., if the site ID is 4410, the third patient screened at 4410 site, would be given the number 4410003).

A patient who is screened but fails to proceed into baseline assessment (e.g., because entry criteria were not met or enrolment did not occur within the specified time frame) may be considered for screening again. Re-screening will be permitted by the site Investigator on a case-by-case basis. A new informed consent form will be signed in any case of re-screening. A new subject ID will be assigned to the subject. Patients who are discontinued will be replaced. Each replacement is by a default a new subject, who will be assigned a completely new subject ID.

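### Section 11.6 halts recruitment on a toxicity model and a TTL that the protocol does not contain, so its only numerical halting condition cannot be applied

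*Protocol*

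**What the plan says.** Section 11.6 gives the Chief Investigator a right to terminate and then lists four conditions under which recruitment must stop:

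1. premature termination of the trial itself;
2. "Drug-related events, i.e. SUSARs, emerging AEs that are serious and the risk/benefit ratio is unacceptable";
3. procedural problems, namely that "the recruitment rate is too low or the number of dropouts for administrative reasons is too high";
4. "The model predicts that the lowest dose has a toxicity above the TTL with 90% certainty".

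Dosing is set elsewhere and follows order of entry. Section 4.1 says: "The first 2 participants will be treated with XBD173 90mg once daily for 8 weeks". Section 5.4 moves patient 3 onwards to twice daily after two weeks, and section 4.1 makes that step depend on the patient having had no grade 2 event.

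Toxicity is handled one patient at a time. Section 4.1 says: "If a grade 2 AE occurs during 90mg once daily dosing, the participant will be withdrawn". Section 4.3.4 lets the investigator discontinue a subject for "Occurrence of an unacceptable Adverse Event due to Grade 2 or above defined by the NCI Common Terminology Criteria for Adverse Events". If twice-daily dosing is not tolerated, section 4.1 leaves the local investigator to stop, reduce or pause it. On numbers, section 4.3.5 says: "Patients who are discontinued will be replaced".

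**The concern.** The fourth condition reads as a Bayesian-style safety stop: a model yields a probability that toxicity at the lowest dose exceeds a limit, and recruitment ends when that probability reaches 90%. Nothing else in the protocol supplies the parts of such a rule. A reader of section 11.6, including an ethics committee, would take it that a quantified toxicity stop is in force when nobody could operate it.

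What is at stake is the study-level response to toxicity that accumulates without becoming serious. Each affected patient on once-daily dosing is withdrawn and replaced, and no stated rule clearly requires anyone to look at the total.

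**Working it through.** **Step 1: what the rule needs, set against what the protocol has.**

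| Element needed | What the protocol provides |
|---|---|
| A lowest dose | Identifiable: 90 mg once daily is the lower of the two regimens (sections 4.1, 5.4) |
| A certainty threshold | 90% (section 11.6) |
| A model | None. The word otherwise refers only to rodent or animal models of pulmonary hypertension (sections 1.1, 1.2). Section 10 is descriptive and unpowered |
| A TTL | Not in the glossary and not used anywhere else; no value |
| A toxicity event | Grade 2 criteria exist for individuals (sections 4.1, 4.3.4), but nothing links them to this rule. Section 3 lists no toxicity outcome |

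The last three elements are all missing, so there is no figure of the plan's own to reproduce.

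**Step 2: could a reader fill the gap by guessing?** As an illustration, take x toxicities in n patients and a Beta(a, b) prior. The rule triggers when P(rate > TTL) is at least 0.90 under Beta(a + x, b + n − x). All inputs here are assumed: TTL from 10% to 40%, and priors Beta(1, 1), Beta(0.5, 0.5) and Beta(0.2, 0.8). The number of toxicities needed to trigger runs from 1 to 4 among four patients and from 2 to 5 among six. The answer depends on inputs the protocol does not state.

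**Step 3: do the other three conditions cover repeated non-serious grade 2 withdrawals?** The first is termination itself. The second speaks of SUSARs and serious events, with a risk/benefit clause. The third counts slow recruitment and dropouts for administrative reasons, and a withdrawal for an adverse event is not administrative. None clearly covers them.

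**Step 4: how a simple count rule would behave.** Take a pause once two participants have been withdrawn for a grade 2 or higher event on once-daily dosing. Let X be the number among the first five starters, with X ~ Binomial(5, p) and q = 1 − p. Then P(X ≥ 2) = 1 − q^5 − 5pq^4.

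| Assumed true rate p | q^5 | 5pq^4 | P(X ≥ 2) |
|---|---|---|---|
| 5% | 0.7738 | 0.2036 | 0.0226 |
| 10% | 0.5905 | 0.3281 | 0.0815 |
| 20% | 0.3277 | 0.4096 | 0.2627 |
| 33% (1/3) | 0.1317 | 0.3292 | 0.5391 |
| 50% | 0.0313 | 0.1563 | 0.8125 |

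The rates are assumptions. One common rate is used although participants 1 and 2 have eight once-daily weeks and later ones two.

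Timing matters too. At the minimum two-week spacing, participant 6 starts at week 5 × 2 = 10. Participant 5 starts at week 8, so that patient's Week 2 visit is due at week 10, within ±3 days. If it falls after participant 6 starts, the figures are an upper bound on pausing before that start.

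**The case against.** The strongest reply is that this is one stray line in an open-label study of at most six patients. It touches no endpoint, dose or analysis and could simply be struck. Much protection remains: the Chief Investigator may terminate, SUSARs and serious events can halt recruitment, starts are staggered, remote data are reviewed twice a week, and section 4.3.4 adds "It is possible that the Sponsor, REC or HRA request termination of the study if there are concerns about conduct or safety". This stands, and it limits the impact.

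A second reply is that a toxicity model can run alongside fixed dosing and might be set out in an analysis plan that is not shown. Such a model is possible in principle. But the protocol makes the halt mandatory, points to no other document for the model or the TTL, and fixes a design in which no step estimates toxicity by dose. The point is a stated decision rule that cannot be carried out, which is more than detail left for later.

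Third, a reader might infer that none of the other conditions could ever catch repeated grade 2 events. The text does not support that. The risk/benefit clause in the second condition can be read as a trigger of its own, and section 8.1 allows important events to be classed as serious on medical judgement. Some repeated grade 2 events could be caught in either way.

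Fourth, a count rule is an addition, and the probabilities describe that rule and not the defect. That is correct. The defect and the case for deletion do not depend on them. A rule limited to once-daily withdrawals would also leave the six twice-daily weeks uncovered, so the proposed rule counts both doses.

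**Conclusion.** The point holds. Of four listed halting conditions, one is numerical, and the three things it still needs (a model, a TTL and a linked toxicity event) are all absent. It cannot be applied as written. Repeated non-serious grade 2 withdrawals are not clearly covered by what is left, and replacement lets enrolment continue past them.

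The impact is limited. A reader might infer that the study has no working safety stop; the documents do not support this, because the serious-event condition and the discretionary powers remain. It is also tempting to say that the line was carried over from a model-based dose-finding template, but the documents do not show where it came from.

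The percentages in the working illustrate once-daily withdrawals only, under assumed common rates. They should not be extended to a fixed total of six, since discontinued patients are replaced and the number of starters is not fixed.

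**What to change.** Delete the fourth condition in section 11.6 and replace it with a rule that site staff can apply, for example: pause recruitment and review if two participants, replaced participants included, have stopped or reduced XBD173 for a grade 2 or higher adverse event at either 90 mg once daily or 90 mg twice daily, checked before each new participant starts. The sponsor should confirm the count of two and say whether events judged unrelated to the drug are excluded. Deletion alone would remove the inoperable rule but would leave accumulating non-serious toxicity largely to discretion.

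The cost is one amended condition, taken through the formal approval that section 11.5 requires, with no extra patients, visits or analyses. The downside is an occasional unnecessary pause. On once-daily withdrawals alone the chance of this is about 2% at an assumed true rate of 5% and 8% at 10%. Counting twice-daily events as well would raise it, and excluding unrelated events would lower it.

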11.7 Funder

This project is funded by Imperial College London.

11.8 Sponsor

Imperial College London will act as the main Sponsor for this study. Delegated responsibilities will be assigned to the NHS trusts taking part in this study.

11.9 Indemnity

Imperial College London will act as the main Sponsor for this study. Delegated responsibilities will be assigned to the NHS trusts taking part in this study

11.10 Record Retention
The site Investigator must retain all study records by the applicable regulations in a secure and safe facility. The site Investigator/institution must take measures to prevent accidental or premature destruction of essential documents, that is, documents that individually and collectively permit evaluation of the conduct of a study and the quality of the data produced, including paper copies of study records (e.g. subject charts) as well as any original source documents that are electronic as required by applicable regulatory requirements.

The site Investigator/institution should retain subject identifiers for at least 10 years after the completion or premature termination of the study. Subject files and other source data must be kept for the maximum period of time permitted by the hospital, institution or private practice, but not less than 10 years. These documents should be retained for a longer period, however, if required by the applicable regulatory requirements. It is the responsibility of PI to inform the institution as to when these documents no longer need to be retained.

If a site Investigator moves, withdraws from an investigation, retires, requests to move records to another location or to assign these records to another party or (e.g. other Investigator) who will accept the responsibility, written notice of this transfer must be made to and agreed upon by each party.

11.11 Confidentiality

Imperial College London holds negligent harm and non-negligent harm insurance policies which apply to this study

11.12 Publications
The expectation is that the study will be published in full in peer reviewed scientific journals. The results may also be published in internal reports and conference presentations

11.13 Audits and Inspections

The study may be subject to audit by Imperial College London under their remit as sponsor and other regulatory bodies to ensure adherence to GCP and the UK Policy Frame Work for Health and Social Care Research.

Assessment Name	Assessment 1 (screening)	Assessment 2 (baseline)	Telephone assessment	Assessment 3	Telephone assessment	Assessment 4	Assessment 5	Assessment 6	Unscheduled visit
Location	Clinic	Clinic/Home	📞	Clinic	📞	Clinic	Clinic	Clinic/Home	Unscheduled assessment
Time (weeks)	Before Week 0	Week 0	Week 1	Week 2	Week 3	Week 4	Week 8	Week 12	Clinic/Home
Assessment Window (days)	0	Within 7 days baseline	± 3 days	± 3 days	± 3 days	± 3 days	± 3 days	± 3 days	when needed
Inclusion/Exclusion criteria	X	-	-	-	-	-	-	-	n/a
Written informed consent	X	-	-	-	-	-	-	-	-
Demographics	X	-	-	-	-	-	-	-	-
Medical and medication history	X	-	-	-	-	-	-	-	X
Physical examination	X	-	-	-	-	X	X	-	X
Concomitant medications	X	X	X	X	X	X	X	X	X
Vital signs	X	-	-	-	-	X	X	-	X
WHO Functional Class	X	-	-	-	-	-	-	-	-
Six-minute walk test (6MWT)	X	-	-	-	-	-	-	-	-
Borg Dyspnoea Index	X	-	-	-	-	-	-	-	-
Haematology blood tests	X	-	-	X	-	X	X	-	X ^b
Clinical chemistry tests	X	-	-	X	-	X	X	-	X ^b
TSPO genotype test	X								
Serum pregnancy test	X ^a	-	-	-	-	-	-	-	-
Urinary pregnancy test		X ^a		X ^a		X ^a	X ^a		X ^a
Home body weight and ankle swelling self-check	-	-	X	-	X	-	-	-	-
XBD173 assay	-	-	-	-	-	X	X	-	-
Research blood samples	-	X	-	X	-	X	X	X	-
Electrocardiogram (ECG)	X	-	-	-	-	X	X	-	-
Administration of XBD173	-	X	-	-	-	-	-	-	X ^b
Review of the diary, XBD173 collection and reconciliation	-	-	-	-	-	X	X	X	-
Report of Adverse Events , if any	-	X	X	X	X	X	X	X	-

Appendix 1: Schedule of Events

^aFor women of childbearing potential.

^bIf clinically required.

[Appendix 2: NCI Common Terminology Criteria for Adverse Events \(adapted\), See separate file](#)
